2.3 Protocol Purpose

This Phase 2 pilot study is a randomized, double-blind, dose response study in 23 subjects comparing the effects of two active doses and a comparator dose of MDMA as an adjunct to manualized psychotherapy. In Stage 1 the study will assess two different active doses (100 mg and 125 mg) and one comparator dose (40 mg) of MDMA, an optional supplemental dose that is half of the assigned dose may be offered to all subjects 1.5 to 2.5 hours after the initial dose. Nine subjects will be randomized to active dose group 1, nine subjects to active dose group 2, and five subjects will be randomized to receive the comparator dose. Stage 1 of the study will consist of two blinded experimental sessions and one open-label experimental session of manualized MDMA-assisted psychotherapy, each lasting six to eight hours and scheduled three to five weeks apart, within a moderate course of non-drug psychotherapy.

The study will be unblinded one month after the second experimental session in Stage 1, after completion of outcome measures, which constitutes the primary endpoint assessment. After unblinding, subjects who received active dose 1 (125 mg MDMA with optional supplemental half dose) during the first two sessions will receive the same active

dose during the open-label third experimental session. Subjects who received active dose 2 (100 mg MDMA with optional supplemental half dose) during the first two sessions will be able to choose, in consultation with the therapist, to either continue to receive active dose 2 during the third session or to increase their dose to active dose 1. The benefit of three versus two active dose sessions will be assessed.

Subjects who received the comparator dose during Stage 1 will have the opportunity to cross over to Stage 2 with three open-label experimental sessions at equivalent time points to Stage 1. Stage 2 will be used to explore the optimal therapeutic dose of MDMA using a clinical titration dosing strategy. The active dose 2 will be administered during the first experimental session and the therapists will choose one of the two active doses of MDMA for the second and third experimental sessions, with an optional supplemental half-dose.

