2.4 Rationale of Dose Selection

This study will compare the effects of psychotherapy sessions assisted by either one of two active doses of MDMA or a comparator dose. The active dose 1 will be 125 mg MDMA followed 1.5 to 2.5 hours later by an optional supplemental dose of 62.5 mg MDMA. The active dose 2 will be 100 mg MDMA followed 1.5 to 2.5 hours later by an optional supplemental dose of 50 mg MDMA. The comparator dose will be 40 mg MDMA followed 1.5 to 2.5 hours later by an optional supplemental dose of 20 mg MDMA. Eighteen of 23 subjects, or 78%, will be assigned to one of the active dose conditions, and five of 23, or 22%, will be assigned to the comparator dose condition. The active dose 1 is equal to the full dose in other MAPS-supported MDMA/PTSD studies.

Subjects in the comparator dose condition during Stage 1 will have the opportunity to cross over to Stage 2. Stage 2 will be used to explore the optimal therapeutic dose using a clinical titration dosing strategy in the second and third Stage 2 sessions allowing for a

choice between two different active doses of MDMA. In Stage 2 subjects will receive an initial dose of 100 mg followed 1.5 to 2.5 hours later by an optional supplemental dose of 50 mg MDMA during the first experimental session. In the second and third session they will receive an initial dose of 100 mg or 125 mg MDMA followed 1.5 to 2.5 hours later by an optional supplemental dose of 50 mg or 62.5 mg, respectively. The decision to titrate the dose in the second and third session will be based on the experience of the first session. If 100 mg MDMA does not seem to be the optimal therapeutic dose based on the first experimental session in Stage 2, the dosage may be increased by an increment of 25 mg in order to achieve the optimal therapeutic dose. The supplemental doses for each experimental session will be half of the initial dose, respectively. The same choice will be provided to Active Dose 2 subjects continuing on to receive a third experimental session in Stage 1 in an open label context.

Table 1. Dose Regimen

Dose	Initial Dose	Optional Supplemental Dose	Min-Max Cumulative Dose	Min-Max Cumulative Dose with Titration
Active Dose 1	125 mg	62.5 mg	125-187.5 mg	N/A
Active Dose 2	100 mg	50 mg	100-150 mg	N/A
Active Dose 2	100 mg	50 mg	100-150 mg	N/A
+ Optional Titration Dose	25 mg	12.5 mg	N/A	125-187.5 mg
Comparator Dose	40 mg	20 mg	40-60 mg	N/A

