5.1.3 Process Measures

All psychotherapy sessions, including experimental sessions, may be recorded to audio and video, with all recordings preserved for research and training purposes.

Adherence criteria and competence ratings will be conducted by qualified, trained blinded adherence raters who will analyze video data from selected preparatory, experimental and integrative sessions. The elements included in adherence criteria are specific to each type of session. These ratings will be collected, at minimum, for each therapist team in the study. The goal of these ratings will be to correlate therapist adherence to the treatment manual with outcome as a part of the sponsor’s ongoing efforts to standardize treatment methods of MDMA-assisted psychotherapy for PTSD.

The SOCQ is a 100-item questionnaire based on the “Peak Experience Profile” designed by Pahnke and colleagues [149, 150]. Subjects respond to the SOCQ using a six-point Likert-type scale anchored at 0=none at all and 5=extreme (more than ever before in my life). It has seven subscale scores; internal unity, external unity, transcendence of time and space, ineffability and paradoxicality (claim of difficulty in describing the experience in words), sense of sacredness, noetic quality, and deeply felt positive mood. The measure is a self-report instrument and takes approximately 20 to 30 minutes to complete. Subjects will complete the SOCQ after each experimental session, at any time between the end of an experimental session and prior to leaving the treatment facility the next day.

Questions regarding the belief of condition assignment and certainty of the belief will be asked of the therapists and subjects at the integrative session on the day after each blinded experimental session in Stage 1. Each therapist responsible for treating the subject will indicate their belief of condition assignment and certainty based on the active doses (125 mg or 100 mg) and comparator dose groups. In line with informed consent obfuscation, where the comparator dose is not revealed, subjects will initially be asked if they believe they received MDMA or not during this assessment. If they believe they received MDMA, they will be asked about what dose they think they received. These beliefs are collected as a part of the sponsor’s ongoing initiative to optimize the double-blind as a part of dose response studies.

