5.3 Randomization and Subject Numbering

Prior to enrollment, subjects will be tracked with their initials and a screening number assigned sequentially starting at “S001”. Subjects who meet all inclusion and no exclusion criteria will be enrolled into the study and will be assigned a five-digit subject number. The first two digits will be “12” and will identify the protocol number. The next three digits identify the subject within the site and will be assigned sequentially, with 001 corresponding to the first subject enrolled, e.g. the first enrolled subject will be 12001, second 12002, etc.

In total, 23 subjects will be enrolled into the study. The randomized portion of the study will be blinded and there will be a 9:9:5 ratio between subjects in the active dose 1, active dose 2, and comparator dose conditions. An unblinded randomization monitor will generate the randomization list. Subjects will be assigned subject numbers, and subjects will be randomized in a blinded fashion. Upon enrolling a subject, the investigator will be provided with an Enrollment Code for that subject. Randomization numbers will be pre-printed on the container labels corresponding to doses for individual sessions. Randomization will be performed at least 24 hours before the experimental session for each subject. The therapists will utilize a web-based randomization program to obtain the container assignment for each experimental session. Blinded personnel will conduct all study evaluations in the randomized portion of the study until the blind is broken for each subject at the primary endpoint per protocol via the web-based randomization program. Detailed instructions will be provided to the site in a separate document.

If there is an emergency requiring knowledge of subject’s condition assignment, the blind may be broken for an individual subject. The investigator may be provided with the condition assignment in case of emergency through the web-based randomization system.

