6.4 Drug Storage and Handling

MDMA is a Schedule I compound and will be stored and handled in compliance with all relevant federal and state regulations. In accordance with these requirements, the Schedule I license holder will be responsible for storing, dispensing, and administering the MDMA. It will be stored in a secure safe in accordance with federal and state regulations.

IP will only be removed for a single experimental session at a time and will be administered orally at the office of the Principal Clinical Investigator (PI). All doses administered will be recorded on the appropriate accountability and administration logs. Only the initial dose is required to be given at each experimental session. Supplemental doses are provided for each experimental session but are optional to use. In addition, the clinical titration doses with corresponding supplemental dose are provided in Stage 2 second and third experimental sessions and are optional to use.

The Schedule 1 License Holder will dispense the appropriate container number for each experimental session. If an optional dose is not administered, the unused capsules will be kept in their respective inner envelopes inside of the primary container in the safe for drug accountability.

Records pertaining to the use of scheduled, regulated compounds will be maintained in accordance with relevant federal and state regulations.

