For exploratory purposes, the sponsor will examine individual PDS, BDI-II, GAF, PSQI, PTGI, and DES-II scores at baseline and the primary endpoint in each active dose and comparator dose conditions. Analysis of variance, or nonparametric analysis if assumptions are not met, will be used to compare the dose conditions for change in BDI-II, PTGI, PSQI, GAF, and DES-II scores separately. If scores cannot be examined sufficiently in this model, then analyses will compare available data through the use of difference scores.

Changes in CAPS from the primary/secondary endpoint to the two-month follow-up in Stage 1/Stage 2 will be compared for a within-subject analysis with p value set at 0.05 to see whether a third session with an active dose produces further decline in symptoms. Stage 2 data will only be combined with open label Stage 1 data for this analysis, if data is equivalent between stages based on confidence intervals. Subjects who receive active

dose 1 in the third experimental session may be compared to subjects who receive active dose 2 for exploratory purposes if at least three subjects are in either group. If less than three subjects from the 100mg group select active dose 2, then analyses will be conducted with and without these subjects to determine the effect of a third session with active dose 1. The sponsor will perform an exploratory within-subject analysis of crossover participants in Stage 2.

A repeated measures analysis of variance (ANOVA) will be performed upon PDS scores at baseline, after each experimental session, and at the end of Stage 1, with p value set at 0.05. Condition will serve as a between-subjects factor. Results of ANOVA analysis will be used to examine the effects of each experimental session on self-reported PTSD symptom severity. PDS and CAPS scores will be correlated via Pearson's product moment correlation at baseline and the primary endpoint to provide a comparison of a self-report measure with a clinician-administered measure of PTSD symptoms.

The sponsor will compute descriptive statistics for SOCQ scores from after each MDMA-assisted psychotherapy session, and average SOCQ scores for blinded experimental sessions will be compared between conditions. The data will be explored for effects of condition on domain scores in the SOCQ.

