6.0 Randomization and Blinding

Per Amendment 6, 26 subjects will be enrolled into the study. The randomized portion of the study will be blinded and there will be a 12:9:5 ratio between subjects in the active dose 1, active dose 2, and comparator dose treatment groups. Subjects will be assigned subject numbers, and subjects will be randomized in a blinded fashion.

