9.9.3.1 Process Measures

States of Consciousness Questionnaire (SOCQ)

Descriptive statistics will be computed for SOCQ scores completed after each MDMA-assisted psychotherapy session, and SOCQ scores will be compared by initial dose using ANOVA for overall differences and t-tests for pairwise comparisons for each experimental session. The data will be explored for effects of dose on composite and total SOCQ scores.

Long-term Follow-up Questionnaire (LTFU Questionnaire)

The LTFU Questionnaire nominal variables will be described in terms of frequencies and percentages, while ordinal and non-normal continuous variables will be described using sample mean, standard deviations, and range.

Belief of Condition Assignment

In order to compare the therapists', independent raters', and subjects' belief of treatment group to actual MDMA dose received in each blinded session, the number and frequency of correct guesses will be calculated and depicted by dose group and study role (subject and each therapist).

Subject's Perceptions of Experimental Sessions

Descriptive statistics will be calculated for subject's perceptions of experimental sessions. Mean, standard deviation and range of individual responses and sum of items #1-4 will be examined. For the 100 and 125 mg group, within-subjects t-tests will be performed on subject's perceptions at Stage 1 primary (visit 12) and end of stage 1 (visit 17) endpoints. The same analysis will be performed for 40 mg group, but data will be from Stage 2 secondary (visit 27) and end of stage 2 (visit 32) endpoints.

Reactions to Research Participation Questionnaire (RRPQ)

Frequency of response will be tabulated for 'reasons for participation' across Stage 1 treatment groups. Descriptive statistics will be computed for total scores for subscales and displayed by Stage 1 conditions.

Adherence to the Treatment Manual

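### Testing SOCQ by initial dose at Stage 1 session 3 (and in Stage 2, if included) compares groups formed by dose choice, so those tests do not estimate a dose effect

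*SAP*

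**What the plan says.** - **SAP 9.9.3.1 (SOCQ):** "SOCQ scores will be compared by initial dose using ANOVA for overall differences and t-tests for pairwise comparisons for each experimental session". The next sentence says that dose effects on the composite and total scores will be explored.
- **Protocol 12.0:** the between-group comparison is narrower: "average SOCQ scores for blinded experimental sessions will be compared between conditions".
- **Protocol 5.1.3:** "Subjects will complete the SOCQ after each experimental session". Scores will therefore exist for Stage 1 session 3 and for all Stage 2 sessions.
- **Meaning of initial dose:** the dose tables in both documents use the term for the first dose of a session, as opposed to the optional supplemental dose. Protocol 6.4 uses it the same way: "Only the initial dose is required to be given at each experimental session".
- **Stage 1 session 3:** Protocol 2.3 keeps the 125 mg arm at 125 mg. Unblinded subjects in the 100 mg arm "will be able to choose, in consultation with the therapist, to either continue to receive active dose 2 during the third session" or go up to 125 mg. Comparator subjects have no session 3 in Stage 1.
- **Stage 2:** Protocol 5.2.9 gives everyone 100 mg at session 1 and allows 100 or 125 mg at sessions 2 and 3. Protocol 2.4 states the basis: "The decision to titrate the dose in the second and third session will be based on the experience of the first session". It then extends the same choice to the 100 mg arm at Stage 1 session 3.
- **Allocation:** SAP 6.0, citing Amendment 6, says "there will be a 12:9:5 ratio between subjects in the active dose 1, active dose 2, and comparator dose treatment groups". The protocol version supplied has "there will be a 9:9:5 ratio between subjects in the active dose 1, active dose 2, and comparator dose conditions". The SAP figure is used below.

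**The concern.** At sessions 1 and 2, grouping by initial dose is the same as grouping by randomised arm. From session 3 the grouping variable is a decision taken after, and possibly because of, earlier drug sessions. SOCQ records the subject's experience of those sessions, so group membership may depend on earlier values of the outcome being tested. The sessions are also open label and SOCQ is self-reported, so expectancy is not controlled.

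The SAP shows awareness of this for the CAPS: section 9.9.3 allows third-session analyses with and without the 100 mg subjects who moved up. SOCQ has no such provision. What is at stake is a set of p-values labelled as dose comparisons, in a group of analyses that SAP 4.2 says are meant to inform future protocol design, when the groups no longer support a dose interpretation.

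**Working it through.** The documents give no SOCQ mean, SD, effect size or power, so there is no stated SOCQ figure to reproduce. The protocol's power figures concern the CAPS and play no part here.

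**Step 1. How the groups are formed.** Let k be the number of the nine 100 mg subjects who stay at 100 mg for session 3.

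| Session | 100 mg group | 125 mg group | Formed by |
|---|---|---|---|
| Stage 1, sessions 1 and 2 | 9 | 12 (plus 5 at 40 mg) | randomisation, blinded |
| Stage 1, session 3 | k who stay | 12 randomised + (9 - k) who move up | choice within the 100 mg arm, open label |
| Stage 2, session 1 | all, at most about 5 | none | no contrast exists |
| Stage 2, sessions 2 and 3 | those kept at 100 mg | those raised | choice, open label |

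**Step 2. Model for session 3.** From the documents: 12 and 9 subjects, two-sided alpha 0.05. Assumed:
- SOCQ has SD 1, with correlation ρ of 0.5 to 0.7 between any two sessions.
- λ is the correlation between a subject's tendency to stay at 100 mg and the mean of that subject's first two SOCQ scores. λ = 0 means choice is unrelated to SOCQ; λ = 1 means the lowest scorers always move up.
- δ is the true 125 minus 100 mg effect, in SD.

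Expected contrast = δ - r λ B(k), where
- r = ρ/√((1+ρ)/2), the correlation of session 3 with the mean of sessions 1 and 2: 0.5/√0.75 = 0.577 and 0.7/√0.85 = 0.759.
- B(k) = S(k)/k + S(k)/(21 - k), where S(k) is the expected sum of the k largest of nine standard normal values, and 21 - k = 12 + (9 - k) is the size of the 125 mg group.

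S(3) = 1.485 + 0.932 + 0.572 = 2.989, and by symmetry S(6) = 2.989. So B(3) = 2.989/3 + 2.989/18 = 1.162 and B(6) = 2.989/6 + 2.989/15 = 0.697.

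| λ | Bias, r = 0.577, 6 stay | Bias, r = 0.759, 3 stay | Expected contrast if δ = +0.5 |
|---|---|---|---|
| 0 | 0 | 0 | +0.50 |
| 0.5 | -0.20 | -0.44 | +0.30 to +0.06 |
| 1 | -0.40 | -0.88 | +0.10 to -0.38 |

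**Step 3. When the sign reverses.** The expected contrast changes sign when rλ exceeds δ/B(k). For δ = 0.3 this is 0.26, 0.35 or 0.58 with 3, 5 or 7 staying (B = 1.162, 0.856, 0.518). For δ = 0.5 it is 0.43, 0.58 or 0.97.

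**Step 4. Simulation with r = 0.7 and 3 of 9 staying.** The wrong-sign column includes ordinary sampling error, which alone gives about 31% when there is no selection.

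| λ | Expected contrast, δ = +0.3 | Wrong sign | Type I error, δ = 0 |
|---|---|---|---|
| -0.6 | +0.79 | 9% | 11% |
| 0 | +0.30 | 31% | 5% |
| 0.3 | +0.06 | 47% | 6% |
| 0.6 | -0.19 | 62% | 11% |
| 1 | -0.51 | 83% | 23% |

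**Step 5. Stage 2, sessions 2 and 3.** With five subjects split 2 and 3, B = 1.38. For δ = 0.3, r = 0.7 and λ = 0.6 the expected contrast is 0.3 - 0.7 × 0.6 × 1.38 = -0.28. The sign is wrong in 63% of simulated trials, against 37% with λ = 0.

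**Step 6. Comparison by randomised arm.** Sessions 1 and 2 carry no selection bias. Session 3 by arm has expectation δ × k/9: for δ = 0.3 this is 0.10, 0.17 or 0.23 with 3, 5 or 7 staying. It is diluted, but it is zero when δ is zero and its expected sign does not reverse.

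**Step 7. Within-subject change in those who move up.** If the lowest scorers move up and there is no dose effect, regression to the mean gives an expected rise of [S/(9 - k)] × √((1+ρ)/2) × [1 - 2ρ/(1+ρ)]. With ρ = 0.7 and six moving, this is 0.498 × 0.922 × 0.176 = 0.08 SD. With ρ = 0.5 and three moving, it is 0.996 × 0.866 × 0.333 = 0.29 SD.

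**The case against.** Much of the opposing case stands.

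- **The SAP keeps the randomised comparison.** Its per-session tests at sessions 1 and 2 are randomised comparisons; only the averaging over the two is dropped. A reader might infer that randomised inference on SOCQ is lost. It is not.
- **Nothing links dose choice to SOCQ.** The choice is made in consultation with the therapists and concerns the best therapeutic dose, whereas SOCQ measures changes in consciousness. Protocol 2.4's account of when to increase is written for Stage 2 and reaches Stage 1 only through the remark that the same choice is offered. A reader might infer that poor responders move up and that the tests will therefore reverse the dose effect. The documents give neither the direction nor the strength of selection.
- **The scope is partly inferred.** The SOCQ paragraph does not name Stage 2, and an overall ANOVA followed by pairwise tests fits three doses, which occur together only at Stage 1 sessions 1 and 2. If initial dose meant the dose first assigned, the session 3 problem would vanish. That reading is less likely, because neighbouring SAP analyses say Stage 1 treatment group when they mean the arm, but it shows that the term needs defining.
- **The consequence is limited.** SOCQ is exploratory. A reader might infer that these tests decide the optimal dose. The documents assign that question to Stage 2 titration and to subjects' perceptions of the sessions, not to SOCQ.

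What remains is that, as written, the SAP plans inferential tests by dose received in sessions where dose is not randomised, and the protocol did not.

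**Conclusion.** The point holds as a fault of specification in an exploratory analysis. At Stage 1 session 3, and at Stage 2 sessions 2 and 3 if they are included, a 100 v 125 mg test by initial dose cannot be read as a dose effect without assumptions about why subjects chose their dose. With no true effect, the bias at session 3 is 0 if choice is unrelated to earlier SOCQ, about -0.2 to -0.45 SD under moderate selection (λ = 0.5), and -0.4 to -0.9 SD if the lowest scorers always move up. Selection in the other direction inflates the contrast. Reversal of a true effect needs fairly strong selection, a small effect, or both; at λ = 0.5 a true +0.5 SD effect stays positive in expectation.

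These sizes rest on assumed correlations of 0.5 to 0.7, three to six of nine staying at 100 mg, and all 12 and 9 subjects reaching session 3. They illustrate the range and do not predict the result. The SOCQ tests at sessions 1 and 2 and the primary CAPS analysis are unaffected.

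**What to change.** In SAP 9.9.3.1:

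1. Restore the analysis in Protocol 12.0: compare SOCQ by randomised arm on the mean of blinded sessions 1 and 2, with each session tested separately if wanted.
2. Define initial dose, and state which sessions and stages are tested.
3. For Stage 1 session 3 and for Stage 2, give descriptive statistics only, labelled non-randomised. Show them by randomised arm, with subjects who moved up and those who did not listed separately. Remove the ANOVA and t-tests by dose received.
4. If the within-subject change of those who moved up is shown, label it descriptive and subject to regression to the mean and open-label expectancy.

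The cost is SAP wording and the loss of a few non-randomised p-values. The change removes a source of bias but adds no precision: two-sided power for 12 v 9 is only 0.10, 0.19 and 0.41 at effects of 0.3, 0.5 and 0.8 SD.
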